### 3. STUDY SCHEDULE OF ASSESSMENTS

**Table 5. Schedule of Events**

Study Day	Screening	Baseline	LYT-100 Patient Cohort Double-Blind Treatment Phase  (N = approximately 50) 										Final Safety Visit
	Day -28 to Day -2	Day -1	Day 1	Week 1	Week 2	Week 4	Week 8	Week 12	Week 16	Week 20	Week 23	Week 26 or Early Termination 	Week 30 (28 days from last dose)
Study Drug			Dose	Dose	Dose	Dose	Dose	Dose	Dose	Dose	Dose	D/C Dose	n/a
+/- Days Allowable		+/-0	+/-0	+/-2	+/-3	+/-3	+/-3	+/-3	+/-3	+/-3	+/-3	+/-3	+/-3
Visit	1	2	(no visit)	3	Phone Call	4	5	6	7	8	Phone Call	9	10
Outpatient Clinic Visit	X	X	(no visit)	X	Phone Call	X	X	X	X	X	Phone Call	X	X
Informed Consent 	X												
Eligibility Assessment	X	X											
Demographics	X												
Medical History 	X												X
12-lead ECG (QTcF) 	X			X				X				X	X
Physical Exam 	X			X				X				X	X
Vital Signs (Height, Weight, BMI, Body Temp, HR, BP, RR) 	X	X		X		X	X	X	X	X		X	X
Bioimpedance 		X		X		X	X	X	X	X		X	
Limb Volume 		X		X		X	X	X	X	X		X	
MoistureMeterD 		X		X		X	X	X	X	X		X	
Tonometry/Skin FibroMeter 		X		X		X	X	X	X	X		X	
Visual Analog Scales		X		X		X	X	X	X	X		X	
LYMPH-Q		X		X		X	X	X	X	X		X	
LYMQOL		X		X		X	X	X	X	X		X	

	Screening	Baseline	LYT-100 Patient Cohort Double-Blind Treatment Phase  (N = approximately 50) 										Final Safety Visit
Study Day	Day -28 to Day -2	Day -1	Day 1	Week 1	Week 2	Week 4	Week 8	Week 12	Week 16	Week 20	Week 23	Week 26 or Early Termination 	Week 30 (28 days from last dose)
Study Drug			Dose	Dose	Dose	Dose	Dose	Dose	Dose	Dose	Dose	D/C Dose	n/a
+/- Days Allowable		+/-0	+/-0	+/-2	+/-3	+/-3	+/-3	+/-3	+/-3	+/-3	+/-3	+/-3	+/-3
Visit	1	2	(no visit)	3	Phone Call	4	5	6	7	8	Phone Call	9	10
Sparse PK Blood Samples 				X		X	X	X	X	X		X	
Concomitant Medication 	X	X		X	X	X	X	X	X	X	X	X	X
Adverse Events 	X	X		X	X	X	X	X	X	X	X	X	X
Pregnancy test 	Urine	Urine						Urine				Urine	
FSH 	X												
Genotyping 		X											
Hematology 	X			X		X		X				X	X
Chemistry 	X			X		X	X	X	X	X		X	X
Coagulation 	X			X		X		X				X	X
Urinalysis	X	X		X		X		X				X	X
Urine Cotinine, drug screen & alcohol breath test	X	X										X	

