10. Concomitant medications include all medications taken 30 days prior to the Screening visit.
11. Adverse events include medical conditions such as infections (e.g., cellulitis and lymphangitis) starting or worsening after LYT-100 or placebo administration. All other medical conditions reported around Screening and Baseline prior to study treatment administration will be reported as pre-treatment AEs.
12. Not required for amenorrhoeic female patients (see below); if a urine pregnancy test is positive, it must be confirmed by a serum pregnancy test.
13. Amenorrhoeic female patients only; postmenopausal status will be confirmed through testing of FSH levels ( $\geq 40$  IU/mL).
14. Patients will provide blood samples at baseline (Day -1) for the determination of CYP1A2, CYP2C9, CYP2C19, and CYP2D6 genotyping – Sample to be obtained on Day -1 of the first period only. Patients are required to provide consent for genotyping.
15. Hematology includes complete blood count and differential.
16. Serum chemistry includes glucose, total protein, albumin, electrolytes (sodium, potassium, chloride, total CO2), calcium, phosphorus, magnesium, uric acid, bilirubin (total, direct), ALT or AST, alkaline phosphatase, creatinine, blood urea nitrogen, creatine phosphokinase (CPK). Liver Function Tests (LFTs) will be collected at each visit and includes bilirubin (total, direct), ALT or AST, and alkaline phosphatase.
17. Coagulation includes international normalized ratio (INR), prothrombin time and APTT.
18. Inflammatory markers include: G-CSF, MIG, FGF-2, IL-4, IL-10, lymphotoxin- $\alpha$ /TNF- $\beta$ , leptin, IL-6, IL-1 $\beta$ , TNF- $\alpha$ , TGF- $\beta$ 1, MMP-9, TIMP-1, MCP-1.
19. Patient completes the Patient Diary starting 1 week prior to each study visit and returns the diary at the end of the week while attending the study visit.
20. Relative limb volume is measured by perometry. Perometry is a non-invasive technique involving a Perometer (Pero-System), which uses infrared light to scan a limb and obtain measurements of the limb's circumference. The truncated cone tape measure method can be used as a backup if the Perometer is unavailable, or not working at time of the patient visit.

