In the ASCEND study ([King et al., 2014](#)), gastrointestinal and skin-related events were more common in the pirfenidone group than in the placebo group; most AEs were assessed as mild to moderate in severity. The incidence of patients discontinuing pirfenidone due to AEs was low (14% of the pirfenidone group; 11% of the placebo group). Excluding patients with worsening

fibrosis, serious AEs were reported in 18.7% of patients in the pirfenidone group and 20.2% of patients in the placebo group.

In the Japanese study (Taniguchi et al., 2010), photosensitivity, anorexia, dizziness, and elevated  $\gamma$ -glutamyl-transpeptidase were significantly more common ( $\geq 5\%$ ;  $p < 0.05$ ) in the high-dose (600 mg TID) group than in the placebo group. Skin-related (photosensitivity, asteatotic eczema) and gastrointestinal AEs (abdominal discomfort) as well as decrease in white blood cells were more common in the low-dose (400 mg TID) group than in the placebo group. Photosensitivity was the major AE observed in 51% of the patients in the high-dose group and 53% in the low-dose group. Of the patients who developed photosensitivity, most had mild events (70% in the high-dose group and 80% in the low-dose group), and the remainder had moderate events. Most of the AEs resolved after decreasing the pirfenidone dose or temporarily withholding the pirfenidone. The incidence of subjects discontinuing pirfenidone due to AEs was low in both dose groups (18% of the high-dose pirfenidone group, 20% of the low-dose pirfenidone group, 13% of the placebo group).

Overall, pirfenidone was well tolerated in the Phase 3 studies. The most common AEs were gastrointestinal AEs (e.g., nausea, dyspepsia, diarrhea, vomiting), fatigue, anorexia, dizziness, rash, and photosensitivity reactions. Serious AEs occurred infrequently and with similar incidence for pirfenidone and placebo subjects. AEs leading to discontinuation of study treatment were infrequent and included nausea, rash, and photosensitivity reactions.

Further information on clinical experience with LYT-100 and pirfenidone is provided in the Investigator's Brochure.

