**Table 10. Hematological Adverse Events Dose Adjustment Guidance**

	Dose modification
ANC <math>\geq</math> 1.0 mm^3	No dose modification
0.5 < ANC < 1.0 mm^3	Stop LYT-100, repeat blood test in 48-72 hrs, or at a clinically indicated time interval, and when resolved to ANC>1.0 then resume at 500mg BID for 3 days followed by 750mg BID  If the same AE repeats, stop LYT-100, repeat blood test in 48-72 hrs, or at a clinically indicated time interval, and when resolved to ANC>1.0 then resume at 500mg BID  If the same AE repeats, discontinue LYT-100 permanently
ANC < 0.5 mm^3	Discontinue LYT-100 permanently
Hgb <math>\leq</math> 8.5 g/dL	Stop LYT-100, clinically manage as appropriate and when Hgb > 10.0 resume LYT-100 at 500mg BID for 3 days followed by 750MG BID  If the same AE repeats, permanently discontinue LYT-100
Platelets > 100,000 mcL	No dose modification

Platelets 50,000-100,000 mcL	
Stop LYT-100 until resolved to >100,000 then resume at 500mg BID for 3 days followed by 750mg BID
 
If the same AE repeats, stop LYT-100, repeat blood at a clinically indicated time interval, and when resolved to >100,000 then resume at 500mg BID
 
If the same AE repeats, discontinue LYT-100 permanently

Platelets < 50,000 mcL	
Stop LYT-100 until resolved to >100,000 then resume at 500mg BID for 3 days followed by 750mg BID
 
If the same AE repeats, permanently discontinue LYT-100

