### **13.7. Visit 6 (Week 12, ± 3 days)**

Patients will attend an onsite visit at the CRU. The following assessments will be performed:

- Visual analog scales
- LYMPH-Q
- LYMQOL
- 12-lead ECG (QTcF), to be collected 2.5 (+/- 15 minutes) after the morning study drug dose
- Symptom directed physical exam
- Concomitant medication
- Adverse events
- Review patient diary
- Bioimpedance
- Limb volume
- MoistureMeterD
- Tonometry/Skin FibroMeter
- Vital signs (weight, BMI, body temperature, HR, BP, RR)
- Study drug dispensing and drug accountability
- Sparse PK blood samples
- Urine pregnancy test: Not required for amenorrhoeic female patients; if a urine pregnancy test is positive, it must be confirmed by a serum pregnancy test.
- Blood hematology
- Serum chemistry (including LFT panel)
- Coagulation
- Urinalysis

Patients will be provided with a quantity of study medication sufficient for self-administration BID until Visit 7.

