### **13.8. Visit 7 (Week 16, ± 3 days)**

Patients will attend an onsite visit at the CRU. The following assessments will be performed:

- Visual analog scales
- LYMPH-Q
- LYMQOL
- Concomitant medication
- Adverse events
- Review patient diary
- Bioimpedance
- Limb volume
- MoistureMeterD
- Tonometry/Skin FibroMeter
- Vital signs (weight, BMI, body temperature, HR, BP, RR)
- Study drug dispensing and drug accountability
- Sparse PK blood samples
- Serum chemistry (including LFT panel)
- Inflammatory biomarkers

Patients will be provided with a quantity of study medication sufficient for self-administration BID until Visit 8.

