### **13.11. Visit 9 (Week 26 $\pm$ 3 days) or Early Termination**

Patients will attend an onsite visit at the CRU. This visit marks the conclusion of the study treatment. The following assessments will be performed:

- Visual Analog Scales
- LYMPH-Q
- LYMQOL
- 12-lead ECG (QTcF)
- Symptom directed physical exam
- Concomitant medication
- Adverse events
- Review patient diary
- Bioimpedance
- Limb volume
- MoistureMeterD
- Tonometry/Skin FibroMeter
- Vital signs (BMI, weight, body temperature, HR, BP, RR)
- Study drug accountability only - no further dispensing
- Sparse PK blood samples
- Urine pregnancy test: Not required for amenorrhoeic female patients; if a urine pregnancy test is positive, it must be confirmed by a serum pregnancy test

- Blood hematology
- Serum chemistry
- Coagulation
- Urinalysis
- Urine drug screen (including cotinine test) and alcohol breath test
- Inflammatory biomarkers

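### Table 10 stops LYT-100 on blood counts, but the last scheduled count that can change dosing is at Week 12, leaving 14 of 26 treatment weeks to discretionary testing

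*Combined protocol and SAP*

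**What the plan says.** **The rule.** Section 9.5, Table 10, ties dosing to three blood counts.
- For a neutrophil count in the intermediate band the instruction is "Stop LYT-100, repeat blood test in 48-72 hrs, or at a clinically indicated time interval". Below the lower limit LYT-100 is ended permanently.
- For low hemoglobin it is "Stop LYT-100, clinically manage as appropriate and when Hgb > 10.0 resume LYT-100", with permanent discontinuation if the event repeats.
- Both low platelet bands require a stop, and repeated events lead to permanent discontinuation.

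**The schedule.** Footnote 15 to Table 5 defines the panel: "Hematology includes complete blood count and differential". That covers all three counts. The Table 5 row marks it at Screening, Weeks 1, 4, 12 and 26 (or early termination), and the Week 30 safety visit.

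The visit lists agree. Section 13.7 (Week 12) lists "Blood hematology", while Sections 13.6, 13.8 and 13.9 (Weeks 8, 16 and 20) do not. Those three lists do have a chemistry entry, beginning "Serum chemistry (including LFT panel", and sparse PK samples. Week 23 is a telephone contact. Of Week 26, Section 13.11 says: "This visit marks the conclusion of the study treatment".

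**Unscheduled tests.** Section 15.1.6 permits additional laboratory tests when the patient's clinical condition is judged to need them. It does not require any.

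**The concern.** A stopping rule based on a laboratory value works only if the value is measured while the drug can still be stopped. Because treatment ends at Week 26, the Week 26 count comes too late to alter dosing. After a normal count at Week 12, nothing on the schedule would reveal a new fall in neutrophils, hemoglobin or platelets during the rest of treatment. Such a fall may cause no symptoms that would prompt a test.

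The protocol handles its other laboratory rules differently. The hepatic and renal rules in Section 9.5 rest on chemistry, which includes liver tests and creatinine and is drawn at Weeks 8, 16 and 20. No reason is given for the difference.

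Two things are at stake. One is patient safety under the protocol's own limits. The other is the primary safety endpoint: Section 8.2 includes hematology in it, and Section 21.4.3 summarizes laboratory values by treatment and scheduled time point. Those tables will hold no scheduled hematology value between Weeks 12 and 26.

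**Working it through.** **1. Reproduce the plan's own count.** The Table 5 hematology row has marks at Screening and Weeks 1, 4, 12, 26 and 30, which is 6. Table 11 budgets 6 hematology samples at 3 mL: 6 × 3 = 18 mL, as stated. Table 5, Section 13 and Table 11 agree, so the empty cells are the intended schedule and not a damaged table.

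**2. On-treatment intervals between scheduled counts.**

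| Interval | Weeks |
|---|---|
| Start to Week 1 | 1 |
| Week 1 to 4 | 3 |
| Week 4 to 12 | 8 |
| Week 12 to 26 | 14 |

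The last interval is 14/26 = 53.8% of treatment, or 98 of 182 days. With a window of ±3 days at each end it runs from 98 − 6 = 92 to 98 + 6 = 104 days (13.1 to 14.9 weeks).

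**3. Chemistry for comparison.** On-treatment chemistry is at Weeks 1, 4, 8, 12, 16, 20 and 26, so the intervals are 1, 3, 4, 4, 4, 4 and 6 weeks.

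**4. Mean delay to the next scheduled test.** Assume that an abnormality starts at a uniformly distributed time over a period of T weeks, persists, and causes no symptoms. With intervals of length L that fill the period, the mean delay is ΣL² / (2T). The onset distribution is my assumption, because the documents give none. Three versions show how far the result depends on it.

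| Assumed onset | Hematology schedule | Chemistry schedule |
|---|---|---|
| Weeks 0–26 | (1 + 9 + 64 + 196)/52 = 270/52 = 5.2 | (1 + 9 + 16 + 16 + 16 + 16 + 36)/52 = 110/52 = 2.1 |
| Weeks 0–12 | (1 + 9 + 64)/24 = 74/24 = 3.1 | (1 + 9 + 16 + 16)/24 = 42/24 = 1.8 |
| Weeks 12–26 | 196/28 = 7.0 | (16 + 16 + 36)/28 = 68/28 = 2.4 |

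The longest possible delay at nominal visit times is 14 weeks for hematology and 6 for chemistry.

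**5. Blood volume.** A count uses 3 mL (Table 11). One at each of the three visits that now lack it would be at most 3 × 3 = 9 mL per patient. Table 11 totals 152 mL, but it counts 10 chemistry and 8 PK samples where Table 5 marks 9 and 7. On Table 5's counts the base is 152 − 5 − 4 = 143 mL. The 9 mL increment is the same on either base.

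**The case against.** The strongest reply is that nothing here is a formal contradiction. Table 5, Section 13 and Table 11 agree with one another. Table 10 is headed as guidance, says what to do once a value is seen, and sets no testing frequency. That is correct. The point is about whether the schedule supports the rule, not about two passages that state different facts.

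A second reply is that the schedule may follow expected risk. Section 9.4 names hepatic, skin and gastrointestinal events as of special interest and no hematological event. The white-cell signal in Section 7.2.2 is thin: the text says "as well as decrease in white blood cells were more common in the low-dose (400 mg TID) group than in the placebo group", and the list for the 600 mg TID group does not include it. The single-dose LYT-100 study saw no significant laboratory changes. This all stands, and it limits how large the risk can be said to be. A single-dose study, however, says nothing about Weeks 12 to 26.

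Three stronger readings are tempting, and the documents do not support them.
- *The rule cannot act after Week 12.* Table 10 acts on any count. Section 15.1.6 allows unscheduled tests, and Section 15.1 gives urgent safety procedures precedence. Adverse events are asked about at Weeks 16, 20 and 23. A low neutrophil count at Week 12 leads to repeat testing, and early termination brings a count. What remains uncovered is a new, symptom-free fall after an acceptable Week 12 count.
- *The safety tables have no hematology data for more than half of treatment.* There are counts at both ends of the interval. A persistent effect would show at Week 26. What is lost is timing, transient changes, and the chance to act.
- *Patients will stay at full dose with dangerous counts.* A patient may already be on a reduced dose, and no passage says how often the limits would be reached.

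**Conclusion.** The gap in scheduled testing is real. Week 12 is the last scheduled count that can trigger the neutrophil, hemoglobin or platelet rules, and 14 of 26 treatment weeks (54%) follow it. None of the existing safeguards would reliably detect a new, symptom-free fall in that time.

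The mean-delay figure is illustrative. It is 5.2 weeks against 2.1 weeks on the chemistry schedule with uniform onset over 26 weeks, and 3.1 weeks if onset falls only in Weeks 0 to 12. In every version the abnormality is assumed persistent and symptom-free. The number of patients affected cannot be estimated, because the documents report no incidence of counts at the Table 10 limits. The point merits correction because closing the gap is cheap, not because a frequent hazard has been shown.

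**What to change.** The sponsor's medical team should reconcile the hematology schedule (Table 5, the Section 13 visit lists and Table 11) with the Table 10 stop rules, so that scheduled counts can support those rules through the treatment period. The testing frequency, the limits and the dose actions are for that team to set.

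Feasibility is not an obstacle. Blood is already drawn for chemistry and PK at Weeks 8, 16 and 20, so no visit or venipuncture need be added. Any count added at those draws would also give the by-visit hematology summaries a scheduled value there.

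The cost is about 3 mL per count, a modest laboratory fee, some incidental abnormal values to review, and edits to the listed tables and sections.

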## 5. LIST OF ABBREVIATIONS AND DEFINITIONS OF TERMS

The following abbreviations and specialist terms are used in this study protocol.

Abbreviation or Specialist Term	Explanation
AE	Adverse Event
ALB	Albumin
ALP	Alkaline Phosphatase
ALT	Alanine aminotransferase
AMP	Amphetamines
APTT	Activated partial thromboplastin time
AST	Aspartate aminotransferase
ATC	Anatomical therapeutic chemical
BAR	Barbiturates
BASO	Basophils
BCRL	Breast cancer-related lymphedema
BICARB	Bicarbonate
BID	Twice daily
BILI	Total Bilirubin
BILIDIR	Direct Bilirubin
BIS	Bioelectrical impedance spectroscopy
BMI	Body Mass Index
BP	Blood pressure
BZO	Benzodiazepines
CA	Calcium
CFR	Code of Federal Regulation
CL	Chloride
C max	Observed maximum plasma concentration
COC	Cocaine
CPK	Creatine phosphokinase
CREAT	Creatinine
CRO	Clinical Research Organization
CRP	C-reactive protein
CRU	Clinical research unit
CSR	Clinical study report
ECG	Electrocardiogram
eCRF	Electronic case report form

Abbreviation or Specialist Term	Explanation
ESN	Eosinophils
FDA	Food and Drug Administration
FGF-2	Fibroblast Growth Factor-2
FNA	Fine needle aspiration
FSH	Follicle-stimulating hormone
GCP	Good Clinical Practice
G-CSF	Granulocyte colony stimulating factor
GGT	Gamma glutamyl transpeptidase
GLOBUL	Globulin
GLU	Glucose
HBsAg	Hepatitis B surface antigen
HCT	Hematocrit
HCV	Hepatitis C virus
HGB	Hemoglobin
HIV	Human immunodeficiency virus
HR	Heart rate
IB	Investigator's Brochure
ICF	Informed Consent Form
ICH	International Council for Harmonisation
IEC	Independent Ethics Committee
IL-10	Interleukin 10
IL-1 $\beta$	Interleukin 1 beta
IL-4	Interleukin 4
IL-6	Interleukin 6
INR	International normalized ratio
IP	Investigational product
IPF	idiopathic pulmonary fibrosis
IRB	Institutional Review Board
IUD	Intrauterine device
IV	Intravenous
IWRS	Interactive Web Response System
K	Potassium
LFT	Liver function test
LYM	Lymphocytes

Abbreviation or Specialist Term	Explanation
LYMPH-Q	Lymphedema Questionnaire- Upper Extremity Module
LYMQOL	Lymphedema Quality of Life Tool, Arm
MCP-1	Monocyte Chemoattractant Protein-1
MDMA	Methylenedioxyamphetamine
MedDRA®	Medical Dictionary for Regulatory Activities
MET	Methamphetamines
MIG	Monokine induced by gamma interferon
MLD	Manual lymph drainage
MM	Medical Monitor
MMP-9	Matrix Metalloproteinase 9
MMRM	Mixed model for repeated measures
MTD	Methadone
n	Number
n/a	Not applicable
NA	Sodium
NEUT	Neutrophils
OCCBLD	Occult Blood
OCP	Oral contraceptive pill
OPI	Opiates
OTC	Over-the-counter
PCP	Phencyclidine
PD	Pharmacodynamics
PHOS	Phosphate
PI	Principal Investigator
PK	Pharmacokinetics
PLAT	Platelets
PP	Pharmacokinetic population
PROT	Protein
PT	Preferred term
QoL	Quality of life
QTcF	QT interval corrected using Fridericia's formula
RBC	Red blood cells
RETI	Reticulocytes
RR	Respiration rate

Abbreviation or Specialist Term	Explanation
SAE	Serious adverse event
SAP	Statistical Analysis Plan
SD	Standard deviation
SOC	System organ class
SPGRAV	Specific Gravity
SRC	Safety Review Committee
TDC	Tissue dielectric constant
TEAE	Treatment-emergent adverse event
TGF- $\beta$ 1	Transforming growth factor beta 1
THC	Tetrahydrocannabinol
TID	Three times a day
TIMP-1	Tissue inhibitor of matrix metalloproteinase 1
TNF- $\alpha$	Tumor necrosis factor alpha
TNF- $\beta$	Tumor necrosis factor beta
TROP1	Troponin 1
U	Urea
UROBIL	Urobilinogen
US	United States
WBC	Leukocytes
WHO	World Health Organization
WOCBP	Woman of childbearing potential

## 7. BACKGROUND AND INTRODUCTION

### 7.1. Introduction

LYT-100 (deupirfenidone) is a selectively deuterated form of pirfenidone. Pirfenidone is an orally active small molecule drug with anti-inflammatory and antifibrotic properties. Pirfenidone has been shown to slow the progression of idiopathic pulmonary fibrosis (IPF) in clinical trials (King et al., 2014; Noble et al., 2011; Rafii et al., 2013; Taniguchi et al., 2010) and has been approved for the treatment of IPF in 30 European countries, Canada, Japan, South Korea, China, India, Argentina, and Mexico and was approved for the treatment of IPF in the United States in 2014. Pirfenidone has been shown to be generally well tolerated; the most common adverse events (AEs) were gastrointestinal symptoms (nausea, diarrhea, dyspepsia, vomiting), fatigue, rash, and photosensitivity reactions.

While pirfenidone has established efficacy in treating fibrotic conditions such as IPF, the short half-life of the drug requires that it be dosed at least three times per day. In addition, metabolism of pirfenidone, primarily by CYP1A2, has the potential to lead to interpatient variability in pharmacokinetics (PK), safety, and efficacy. To address the possible limitations of pirfenidone, a selectively deuterated form of pirfenidone (referred to as LYT-100) has been developed. LYT-100 was designed by substituting three deuterium atoms for hydrogen at the methyl group in the pirfenidone molecule, with the objective of attenuating the rate of drug metabolism and improving the overall PK profile of the drug. LYT-100 is expected to be metabolized more slowly compared with non-deuterated pirfenidone. The possibility of less frequent dosing with LYT-100 therapy and slowed rate of drug metabolism may result in improved tolerability and efficacy compared with pirfenidone.

PureTech LYT 100, Inc. intends to study LYT-100 for the treatment of lymphedema, a chronic condition that is characterized by swelling due to the build-up of lymph fluid and tissue fibrotic remodeling. Lymphedema is a progressive fibrotic and inflammatory disease, and there is no approved pharmacologic therapy for lymphedema. LYT-100 has both anti-fibrotic and anti-inflammatory activity based on *in vitro* and *in vivo* models of fibrotic and inflammatory conditions. Existing treatments focus on reducing the symptoms and using mechanical compression to prevent swelling. However, these treatments do not address the underlying mechanisms of lymphedema and are required chronically for management of the condition. Millions of people worldwide are affected by secondary lymphedema (Rockson et al., 2019), and each year up to 15% of cancer survivors with malignancies ranging from melanoma to sarcoma will develop lymphedema (Cormier et al., 2010). As such, there is an unmet medical need for developing safe and effective new treatments for lymphedema.

The purpose of this study is to evaluate the safety, tolerability, PK, and effect on secondary clinical endpoints of LYT-100 administered twice daily (BID) for 6 months in breast carcinoma patients with secondary lymphedema following axillary node dissection and/or sentinel lymph node biopsy, with or without radiation.

